4. STUDY DESIGN

4.1. Study type

This is a diagnostic study evaluating the diagnostic accuracy of the Ultra assay in stools with a two-stage sequential design starting as a cohort of children with presumptive TB enriched in a second stage with Ultra positive TB cases on respiratory sample. It is both an ancillary to the TB-Speed HIV and the TB-Speed SAM studies and a study enrolling children from routine not enrolled in those two studies.

This design was chosen to be able to evaluate the sensitivity and specificity of the Ultra assay in a smaller sample size that is usually required by a "classical" prospective cohort design and avoiding the bias of overestimation of the sensitivity classically associated with the case-control design. In order to quickly generate data on appropriate stool processing method, and to contribute to the planned WHO recommendations for stool Ultra testing (expected 2nd semester 2021), we will use a two-stage sequential design. Indeed, knowing that on average only 10-15% of children with presumptive TB in a community-based setting will be confirmed, in order to reach the sample size of confirmed cases for the evaluation of sensitivity, 7 to 10 times more children with presumptive TB would need to be enrolled in a prospective design. On the other hand, the number of children with presumptive TB not confirmed with TB for the estimation of the specificity would be reached much earlier. In addition, based on the previous study results, we know that the specificity of Xpert MTB/RIF assay in stool is high (99% CI:98-99; [32]), which would result in a relatively small sample size to evaluate the specificity of the Ultra in stools.

During the first stage, we will offer to join all consecutive presumptive TB cases presenting at study sites to estimate specificity with the expected precision and calculate a preliminary sensitivity estimate. During the second stage, we will keep enrolling only those from TB Speed studies and routine care who are Xpert positive on respiratory samples in order to estimate sensitivity with the expected precision.

This two-stage sequential design first estimating specificity then sensitivity has been described by Wruck *et al.* [43] as an efficient way of validating diagnostic tests when the prevalence of the disease is low. It would not be feasible to consecutively enrol all children with presumptive TB to describe an expected sensitivity of 60% with 10% precision as this would require over 900 patients, of which, approximately 800 would be culture negative. In the two-stage process described by Wruck, only reference standard positive samples from the original population are selected in stage 2. We adapted this design to the TB context as culture results will only be available after enrolment (and if the child is positive, only after they have started treatment), hence selecting only those who are Ultra positive on respiratory samples for the second cohort as a way of enriching the study population with a subpopulation that has a higher TB prevalence probability, before their true disease status

is confirmed. Other comparable diagnostic studies have either used greater resources to include larger samples sizes (Dorman [14] and Wang [44]) or have resorted to reporting imprecise estimates of sensitivity [79-84]. To our knowledge, this is a relatively unique approach to study design for accuracy studies, with few published examples [45,46].

With such design, there should be no bias on the evaluation of the specificity similarly to a classical prospective design because this evaluation will be done among consecutively enrolled children with presumptive TB only. The sensitivity estimates may not be generalizable to all culture confirmed TB children due to the sampling approach. Xpert positive children will be more likely to have higher biological loads, causing a possible inflation of the sensitivity. However, the results will provide valuable information on variations of sensitivities of the different stool processing methods within this population.

We will carry out an interim analysis after the completion of the prospective cohort in order to describe specificity and preliminary results of the sensitivity and the agreement between the processing methods. The recruitment of participants will not be put on hold during the interim analysis. We will conduct a final analysis at the end of the study to describe sensitivity as well as the secondary end points.

4.2. Methodology

Enrolment will have 2 stages. During stage 1 (prospective cohort stage), all consecutive children with presumptive TB enrolled in the TB-Speed HIV or TB-Speed SAM or seen in routine care if ineligible for those two studies will be proposed to participate in the study until we reach the number needed for the evaluation of specificity. All children with presumptive TB will have at least two respiratory samples collected (ES or GA) tested with Ultra and mycobacterial culture. The cohort will be closed once the sample size of presumptive TB children with two negative Ultra results from respiratory samples will be reached.

During the 2nd phase (enrichment phase), only children with presumptive TB who are Xpert positive on at least one respiratory sample will be proposed to participate in the study in order to complement the number of confirmed TB cases required for the evaluation of the sensitivity.

TB-Speed SAM and HIV studies

TB–Speed SAM is a multicentric prospective diagnostic cohort study aiming to assess several diagnostic tests that could result in the development of a score and algorithm for TB treatment decision in hospitalised children with severe acute malnutrition (SAM). It will enrol 720 children <5 years old with WHO-defined severe acute malnutrition in Uganda and Zambia.

TB-Speed HIV is a Prospective, multicentre management study evaluating the safety and feasibility of the recently proposed PAANTHER TB treatment decision algorithm for HIV-infected children with presumptive TB. 550 HIV-infected children aged <15 years with clinically suspected (presumptive) TB will be enrolled from Côte d'Ivoire, Uganda, Mozambique and Zambia.

Prospective cohort:

Any child with presumptive TB will be proposed to participate in the study.

If the child is enrolled in the TB Speed SAM or HIV studies, the study nurse will collect two stool samples then collect information about the clinical examination, chest X-ray, HIV-testing and the mycobacterial culture results as soon as they are available, from the data collected in the TB-Speed records since all these procedures are already performed in these studies.

For children identified from the routine practice in the two hospitals, the nurse will collect two respiratory samples (sputum or GA) in consecutive children with presumptive TB to be tested using Ultra as done in routine care, record symptoms and refer the child for clinical exam and for chest X-ray. For the purpose of the study, two stool samples will be collected to be tested with Ultra. In addition, for study purpose the two respiratory samples will be tested with Mycobacterial culture as this test is not routinely prescribed for TB diagnosis in the study sites. However, culture results will be made available to the clinicians for case management. HIV-testing will be offered for children with unknown status as done under routine practice in both sites.

Xpert positive enrichment cohort:

Any child with presumptive TB and a positive Xpert result (MTB/Rif or Ultra according local practice) from one respiratory sample (NPA, IS or GA) will be proposed to participate in the study.

If the child is enrolled in the TB-Speed SAM or HIV studies, the study nurse will then collect two stool samples as well as information about the clinical examination, chest X-ray, HIV-testing and the mycobacterial culture

results from respiratory samples as soon as they are available, from the data collected in the TB-Speed records since all these procedures are already performed in these studies.

For children identified from the routine care in the three hospitals, once enrolled, samples collected as routine practice will be tested with mycobacterial culture in addition to Xpert. If needed, in case there is no enough sample volume remaining for culture after Xpert or if only one sample was collected because the first sample is Xpert positive, an additional respiratory sample will be collected (sputum or GA) and tested with Mycobacterial culture. The nurse will also record symptoms, refer the child for clinical exam and for chest X-ray, and collect stool samples. HIV-testing will be offered for children with unknown HIV-status. The two stool samples and additional respiratory samples if necessary will be collected for the purpose of the study only. However, culture and drug susceptibility results from the respiratory samples will be made available to the clinician for case management.

4.3. Sample size

As we want to estimate two proportions, specificity and sensitivity, we need to ensure a sufficient sample size for these two estimates.

The first stage is to estimate specificity by enrolling children with presumptive TB. With an expected specificity of Ultra in stool of 90%, the minimum sample size to estimate specificity with 5% precision, is 140 children with presumptive TB and negative TB culture from two respiratory samples. Inflating this number by 15% for attrition (to a total of 160 children) and considering a 10% prevalence of culture-confirmed TB in our population, we will need to enrol a total of 177 children with presumptive TB.

The second stage is to estimate sensitivity among presumptive TB children with culture confirmed TB. With an expected sensitivity of Ultra in stool of 60%, based on a literature review, the minimum sample size to estimate sensitivity with 10% precision, is 93 children with culture-confirmed TB. Inflating this number by 10% for attrition and invalid results, we will need a total of 103 confirmed TB cases. We expect 16 culture confirmed to be enrolled during the first stage (10% of 160 children enrolled in the prospective cohort). Then we will need to enrol an additional 87 children during the 2nd stage from presumptive TB children with a respiratory sample positive with Xpert Ultra (enrichment cohort). Knowing that only 90% of these children will ultimately be culture positive, we will need to further inflate the number of children to be recruited based on Ultra result in their respiratory sample [84]. We will therefore a total of enrol 97 children with Xpert Ultra positive results during the second stage.

Given routine site data and estimated enrolment figures for the Ugandan and Zambian study site, we expect to enrol children for the first stage in approximately 12 months, and Ultra-positive children for the second stage in 11 months.

For the secondary endpoints, in order to test Kappa coefficients with a minimum acceptable value of 0.4 [47], considering the study sample size, we will be able to detect a minimum change of 0.1 in Kappa coefficient between the stool sample processing methods with 80% power.

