11.2. Description of the statistical analysis plan

11.2.1. Analysis of the primary endpoint

Sensitivity of the 4 Ultra on stool using TB culture reference standard (LJ and MGIT) in respiratory sample: point estimate and 95% CIs.

Specificity of the 4 Ultra on stool using TB culture reference standard (LJ and MGIT) in respiratory sample: point estimate and 95% CIs.

We will use as TB culture reference standard:

- Positive: at least one positive MTB culture result in one of the two respiratory samples
- Negative: negative culture results from 2 samples without any positive result

An intention-to-diagnose analysis will be performed at:

- Sample level (denominator: total number of samples collected): 1 stool vs the TB culture reference standard
- Patient level (denominator total number of cases with at least one stool sample collected): at least 1 of the two stools vs the TB culture reference standard.

A patient will be classified as stool positive, when they have at least one positive stool Ultra result (for example the first stool may not have any positive Ultra results, but the second stool could have 1 positive Ultra result, in which case the patient would be considered stool positive).

Invalid Ultra results, contaminated and NTM culture results will be considered negative.

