 as preliminary results of the sensitivity and the agreement between the processing methods.
- A final analysis will be conducted at the end of the study to describe sensitivity as well as the secondary end points.
- Follow-up: children will be followed up for 2 months upon enrolment, regardless of their TB diagnosis with protocol visits at day 1 and month 2.

Sample size: 274 children (below 15 years old)

- Inclusion criteria (prospective cohort):
- Children < 15 years of age
- Presumptive intra-thoracic TB based on at least one criterion among the following:
 - Persistent cough for more than 2 weeks
 - Persistent fever for more than 2 weeks
 - Recent failure to thrive (documented clear deviation from a previous growth trajectory in the last 3 months or Z score weight/age < 2)
 - o Failure of broad-spectrum antibiotics for treatment of pneumonia
 - Suggestive CXR features

OR

- History of contact with a TB case and any of the symptoms listed under point 2 with a shorter duration (< 2 weeks) if the child is HIV infected or present a SAM.
- Signed informed consent by parent or guardian and assent signed by children > 7 years old.

Inclusion criteria (enrichment cohort):

- Children < 15 years of age
 - Presumptive intra-thoracic TB based on at least one criterion among the following:
 - Persistent cough for more than 2 weeks
 - Persistent fever for more than 2 weeks
 - Recent failure to thrive (documented clear deviation from a previous growth trajectory in the last 3 months or Z score weight/age < 2)
 - o Failure of broad-spectrum antibiotics for treatment of pneumonia
 - Suggestive CXR features

OR

- History of contact with a TB case and any of the symptoms listed under point 2 with a shorter duration (< 2 weeks) if the child is HIV infected or present a SAM.
- One positive Xpert (MTB/Rif or Ultra) result from at least one respiratory sample: sputum or GA .

- Signed informed consent by parent or guardian and assent signed by children > 7 years old.

Non-inclusion criteria: Antituberculosis treatment > 5 days in the last 3 months, History of tuberculosis preventive treatment in the last 3 months, confirmed extrapulmonary TB only.

Trial agenda:

- First enrolment: January 2020
- End of prospective cohort enrolment: January 2021
- Interim-analysis: April 2021
- Start of enrichment cohort enrolment: January 2021
- · End of enrichment cohort enrolment: December 2021
- End of follow-up: February 2022
- Analysis-report: May 2022

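### Section 4.3 uses 160 both as a culture-negative count and as stage-1 enrolment (177), so the expected 16 cases, the stage-2 figure of 97 and the total of 274 are each off by about two

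*Protocol*

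**What the plan says.** Protocol section 4.3 builds stage 1 in three steps.

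- Precision: specificity is assumed to be 90%, and on that basis the plan states that "the minimum sample size to estimate specificity with 5% precision, is 140 children with presumptive TB and negative TB culture from two respiratory samples".
- Attrition: "Inflating this number by 15% for attrition (to a total of 160 children").
- Prevalence: "considering a 10% prevalence of culture-confirmed TB in our population, we will need to enrol a total of 177 children with presumptive TB".

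The stage-2 paragraph requires 93 culture-confirmed cases, raised to 103 for attrition and invalid results. It then credits stage 1 with part of that number: "We expect 16 culture confirmed to be enrolled during the first stage (10% of 160 children enrolled in the prospective cohort"). The remainder is 87 cases. Because 90% of Ultra-positive children are expected to be culture positive, this becomes 97 children to enrol in stage 2. Appendix 1 gives the overall figure: "Sample size: 274 children (below 15 years old").

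**The concern.** The number 160 carries two meanings that cannot both hold. In the stage-1 paragraph it counts culture-negative children after the attrition allowance, so confirmed cases are excluded from it by definition. In the stage-2 paragraph it is the whole enrolled cohort, from which 10% are expected to be confirmed. The enrolled cohort is 177, and Appendix 1 agrees, since 274 = 177 + 97. The slip passes into every later figure in the chain.

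A second, smaller point concerns the attrition step. The stated minimum is 140 evaluable culture-negatives, and section 4.3 does not say how much loss 177 can absorb before that minimum is missed. Specificity is half of the primary endpoint, and this section is where its sample size is justified, so the figures should agree with one another.

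**Working it through.** **Inputs** (section 4.3 unless noted): specificity 0.90; precision 0.05, taken as the half-width; 95% confidence, from section 11.2.1; 140 culture-negatives; 15% attrition allowance; 10% prevalence; 103 confirmed cases needed; 90% of Ultra-positive children culture positive.

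**Reproducing the plan's stage 1**

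- n = 1.96² × 0.90 × 0.10 / 0.05² = 138.3 (the plan gives 140).
- 138.3 × 1.15 = 159.0, and from 139 it is 159.9 (the plan gives 160).
- 138.3 × 1.15 / 0.90 = 176.7, so 177, as stated.

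**Reproducing the plan's stage 2**

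- 10% × 160 = 16.
- 103 − 16 = 87.
- 87 / 0.90 = 96.7, so 97.
- 177 + 97 = 274, as in Appendix 1.

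**Same chain, with prevalence applied to the children enrolled**

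- 10% × 177 = 17.7, about 18.
- 103 − 18 = 85 (unrounded, 103 − 17.7 = 85.3).
- 85 / 0.90 = 94.4, and 85.3 / 0.90 = 94.8; both round up to 95.
- 177 + 95 = 272.

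**What 177 leaves for specificity**

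Culture-negatives enrolled: 177 × 0.90 = 159.3.

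| Reading of the 15% | Evaluable culture-negatives | 95% half-width at 90% specificity |
|---|---|---|
| Loss of 15% | 159.3 × 0.85 = 135.4 | 1.96 × √(0.09/135.4) = 5.05 points |
| Factor of 1.15 | 159.3 / 1.15 = 138.5 | 1.96 × √(0.09/138.5) = 5.00 points |
| Stated minimum | 140 | 1.96 × √(0.09/140) = 4.97 points |

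The largest loss that still leaves 140 is 1 − 140/159.3 = 12.1%.

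**The case against.** **Attrition.** A reader might infer that the plan multiplied where it should have divided, and that stage 1 must therefore grow to 140/(0.85 × 0.90) = 183.0, or 184 when rounded up at each step. The protocol does not support that as a requirement. It speaks of inflating by 15%, which is literally a factor of 1.15, and it states no 15% loss rate. On its own wording 177 leaves 138.5 children against the 138.3 that the formula needs. The benchmark of 140 is itself rounded up.

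**Rounding.** A reader might also infer that 160/0.9 = 177.8 was cut down to 177. The unrounded chain gives 176.7, which rounds up to 177, so that is not shown.

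**Practical risk to specificity.** The 90% assumption is cautious beside the protocol's own citations: 99% for stool Xpert MTB/RIF (section 4.1), and 96.9% and 98.1% for Ultra in children (section 1). None of these is stool Ultra, so a range is fairer. With 135 children the half-width is about 3.7 points at 95% specificity and 2.9 at 97%. Under section 11.2.1, invalid Ultra results and contaminated or NTM cultures count as negative, so they do not shrink the primary denominator.

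**Closing rule.** Section 4.2 closes stage 1 on a count of children with two negative respiratory Ultra results, so 177 is a planning figure and not a cap. That is fair. However, the rule counts Ultra-negatives, not evaluable culture-negatives, so it does not by itself secure 140.

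**The 16 cases.** One could defend 16 as a figure net of losses, since 17.7 × 0.9 = 15.9. The text does not say this. It derives 16 from 160 enrolled children, and 103 already contains the allowance for attrition. What does stand is that the undercount runs in the safe direction for sensitivity.

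**Conclusion.** The double use of 160 is a genuine inconsistency and depends on no convention. On the protocol's own inputs stage 1 should yield about 18 confirmed cases, not 16. The remaining need is then about 85 rather than 87, stage 2 about 95 rather than 97, and the total about 272 rather than 274. The present figures ask for about two children more than needed, so sensitivity is not weakened.

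On attrition, 177 falls just below the stated minimum of 140 under either reading of the 15%: about 135 or about 138.5. The cost is at most 0.05 points beyond the 5-point target, assuming 90% specificity, 10% prevalence and a normal-approximation interval. That is negligible. The documents do not support concluding that the specificity estimate is inadequately sized or that stage 1 must be enlarged. This is a correction to the stated figures and leaves the design as it is.

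**What to change.** In section 4.3:

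- Compute expected stage-1 confirmed cases from the 177 enrolled (about 18), and reserve 160 for the attrition-inflated culture-negative count.
- Restate 87 as about 85 and 97 as about 95.
- Keep 177, and state either that it tolerates about 12% attrition while leaving 140 evaluable culture-negatives, or that at 15% loss it gives about 135 (±5.1 points at 90% specificity).

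In Appendix 1, restate the total of 274 as about 272.

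The cost is a few sentences in two places. No further enrolment is called for, and the stage-2 target falls by about two children.

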11.2.2. Analysis of secondary endpoints

- Per-protocol analysis of sensitivities and specificities of Ultra on stool using TB culture reference standard (LJ ans MGIT) in respiratory sample, excluding invalid Ultra results, contaminated and NTM culture results from analysis. Regarding contamination, since two culture methods will be used per respiratory sample (LJ and MGIT), to be excluded both culture results per sample will need to be contaminated.
- Head to head comparison of the sensitivities and specificities between the different stool processing methods using culture reference standard and McNemar test for matched data:
 - Sucrose flotation classic method vs Sucrose Flotation optimised method
 - Sucrose flotation classic method vs SPK method
 - Sucrose flotation classic method vs STEP method
 - Sucrose flotation optimised method vs SPK method
 - Sucrose flotation optimised method vs STEP method
 - SPK method vs STEP method
- Head to head comparison of the sensitivities and specificities between the different stool processing methods using the TB composite reference standard as defined by Clinical Case Definition for Classification of Intrathoracic Tuberculosis in Children, and McNemar test for matched data:
 - Sucrose flotation classic method vs Sucrose Flotation optimised method
 - Sucrose flotation classic method vs SPK method
 - Sucrose flotation classic method vs STEP method
 - Sucrose flotation optimised method vs SPK method
 - Sucrose flotation optimised method vs STEP method
 - SPK method vs STEP method
- Description of results for rifampicin resistance using stool Ultra, respiratory Ultra, LPA and DST
- Agreement of the different stool sample processing methods for Ultra detection head to head using Kappa analysis.
- Comparison of the proportion of rifampicin resistance indeterminate Ultra test results between different stool processing methods using McNemar test for matched data.
- Comparison of the proportion of invalid Ultra test results between different stool processing methods using McNemar test for matched data.
- Comparison of the proportion of Ultra results "trace" between the methods using McNemar test for matched data.
- Proportion of very low, low, medium and high Xpert Ultra results by different methods

- Change in sensitivity and specificity at patient level by using 2 stools vs using just the 1st stool specimen for each processing method.

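### Section 4.3 claims 80% power for a 0.1 change in Kappa from 0.4; under a 5% test, 274 children give about 32–44% two-sided (44–56% one-sided)

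*Protocol*

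**What the plan says.** The power statement closes Protocol section 4.3. It concerns the secondary endpoints, gives its starting point as "in order to test Kappa coefficients with a minimum acceptable value of 0.4", refers to the study sample size, and concludes that "we will be able to detect a minimum change of 0.1 in Kappa coefficient between the stool sample processing methods with 80% power".

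The study sample size comes from the same section. For stage 1, "we will need to enrol a total of 177 children with presumptive TB"; for stage 2 the plan is to "enrol 97 children with Xpert Ultra positive results during the second stage". The sum, 274, is the total in the study summary (Appendix 1).

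The analysis to which the statement refers is listed in section 11.2.2: "Agreement of the different stool sample processing methods for Ultra detection head to head using Kappa analysis". No alpha, sidedness, share of positive stools, unit (child or stool) or formula is given for the power figure. The nearest indication of an error level is in section 11.2.1, where the primary endpoint is reported as "point estimate and 95% CIs".

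**The concern.** A change of 0.1 in Kappa is small against the sampling error of Kappa in a few hundred children, so 80% power at 274 looks too high on its face. This is a stated result that can be checked, not a detail left for later.

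Comparing four processing methods in the same children is the purpose of the study, and agreement between them is also to be described at the interim analysis. A reader who sees similar Kappas could take the similarity as backed by 80% power when the design has roughly half that on a two-sided test.

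**Working it through.** **Inputs from the protocol**
- Null Kappa κ0 = 0.4, change 0.1 (so κ1 = 0.5), stated power 80%: section 4.3.
- n = 274 children: 177 + 97, section 4.3 and Appendix 1.
- Two stools per child (section 6.3), so at most 548 stools.
- For positivity: 103 confirmed cases, expected sensitivity 60%, expected specificity 90%, all in section 4.3.

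**Assumptions, because the protocol is silent**
- 5% test, two-sided (in line with the 95% intervals elsewhere) and one-sided.
- Implied positivity: 103 × 0.60 + 171 × 0.10 = 61.8 + 17.1 = 78.9, and 78.9/274 = 28.8%. Range tried: 20–50%.
- Equal positivity for the two methods, then relaxed.

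**Check on the section's other figures.** 1.96² × 0.9 × 0.1/0.05² = 138 and 1.96² × 0.6 × 0.4/0.1² = 92, against 140 and 93 stated. The precision-based sample sizes for the primary endpoint reproduce. The Kappa power does not.

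**Formula** (goodness-of-fit test of Kappa for two binary ratings). With p the positivity, q = 1 − p and d = [pq(κ1 − κ0)]²:

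S = d/(p² + pqκ0) + 2d/[pq(1 − κ0)] + d/(q² + pqκ0)

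n = (z_α + z_β)²/S; power = Φ(√(nS) − z_α)

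**At p = 0.288**
- pq = 0.2051; d = 0.02051² = 0.000420.
- S = 0.00255 + 0.00684 + 0.00071 = 0.01010.
- √(274 × 0.01010) = 1.663.
- Two-sided power = Φ(1.663 − 1.960) = 0.38; one-sided = Φ(1.663 − 1.645) = 0.51.
- n for 80% power, two-sided = (1.960 + 0.842)²/0.01010 ≈ 778.

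**Over the range of positivity** (two-sided / one-sided)

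| Positivity | n needed for 0.1 at 80% power | Power, 274 children | Change detectable at 80%, 274 children | Power, 548 stools taken as independent |
|---|---|---|---|---|
| 20% | 963 / 758 | 0.32 / 0.44 | 0.187 / 0.166 | 0.56 / 0.68 |
| 28.8% | 778 / 613 | 0.38 / 0.51 | 0.168 / 0.149 | 0.65 / 0.76 |
| 40% | 682 / 537 | 0.43 / 0.55 | 0.158 / 0.140 | 0.71 / 0.81 |
| 50% | 660 / 520 | 0.44 / 0.56 | 0.155 / 0.138 | 0.72 / 0.82 |

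**Cross-checks at 274 children**
- Multinomial simulation gave two-sided power of 38% at 27% positivity and 45% at 50%.
- A Wald test with the large-sample (Fleiss) variance gave 33–37% at 23–29% positivity and 44% at 50%, two-sided.
- Letting the two methods differ strongly in positivity raised the maximum to about 57% two-sided and 69% one-sided.

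**Precision.** The standard deviation of the estimate near Kappa 0.4 is 0.1/√(nS) = 0.1/1.663 = 0.060. The 95% interval is therefore about ±0.12 at 28.8% positivity, and ±0.13 to ±0.11 over 20–50%.

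**The case against.** **The unit may be the stool.** Section 11.2.1 analyses the primary endpoint at sample level as well as patient level, and section 11.2.2 gives no unit for Kappa. With 548 stools and a one-sided 5% test, power is 81–82% at 40–50% positivity. The stated 80% could therefore come from an unstated unit and sidedness rather than from a slip. This stands as a possible origin of the figure but does not support it: it needs three unstated choices together, it treats two stools from one child as independent, and at the protocol's implied positivity it gives 76%.

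**The wording may mean a difference between two Kappas.** A reader might infer that comparing two dependent Kappas would have less power still. That does not follow. Simulated power for 0.4 against 0.5 between two pairs sharing a method was 29–58% two-sided and 41–70% one-sided, which overlaps and partly exceeds the single-Kappa figures. The answer depends on the correlation between the two estimates. If that correlation is simply set at 0.8, two-sided power is 74% at 27% positivity and 83% at 50%. The protocol states no such correlation, so this reading neither worsens the point nor rescues the claim.

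**The cited source is not available.** Section 4.3 refers to a paper on Kappa sample-size requirements that cannot be consulted here, so the authors' exact calculation is unknown. This is a reason to give ranges and ask for the inputs.

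**The consequence is limited.** This stands. The objective in section 2.2 is to describe agreement, the interim analysis likewise describes it, and section 11.2.2 names McNemar tests for the method comparisons but no hypothesis test for Kappa. A reader might infer that the trial is under-sized or that a planned test will fail. The documents support neither: no Kappa test is specified, and enrolment is set by the precision targets for sensitivity and specificity.

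**Conclusion.** The 80% figure is not supported as written. For a 5% test of Kappa 0.4 against 0.5 in 274 children with 20–50% positive stools, power is about 32–44% two-sided and 44–56% one-sided. The design detects a change of about 0.155–0.187 (0.138–0.166 one-sided) with 80% power.

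The exact shortfall rests on an alpha, sidedness, positivity and unit that the protocol does not give, so no single power value should be quoted as the true one. The existence of a shortfall is firmer: every child-level test of a single Kappa against 0.4 that was tried stays below 80%, including very unequal positivity. This is a correction that should be made to a descriptive secondary endpoint. It does not affect the primary endpoint or the number of children enrolled.

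**What to change.** Change the last sentence of section 4.3 in one of two ways.

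1. **Keep a power statement.** Give the power or detectable change that the design delivers, with alpha, sidedness, assumed positivity, unit of analysis and formula. For example: *With 274 children, a two-sided 5% goodness-of-fit test of Kappa = 0.4, one result per child and method, and 29% of results positive, a Kappa of about 0.57 is detectable with 80% power; power for a Kappa of 0.5 is about 38%.* If stools are the intended unit, say so and allow for two stools per child. If a difference between two Kappas is intended, state the correlation assumed.
2. **Drop the power claim.** This suits the descriptive objective better. State the expected precision, a 95% interval of about ±0.12 around a Kappa of 0.4, and report each pairwise Kappa with its 95% interval.

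Either costs one sentence and no extra children. The only loss is a less favourable figure on paper.
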